Advanced cDNA Synthesis Kit; Bio-Rad or equivalent) and a TaqMan® microRNA RT kit (Applied Biosystems, Foster City, CA, USA) or equivalent. Individual Taqman® probes (Applied Biosystems) or microarray (Qiagen) will be used to determine the mRNA expression of intramuscular molecular regulation to include but not limited to, PGC-1α, PPARs, SIRT1, p53, CPT1a, FABP, FAT, TNF-α, TNF-αR, IL-6, IL-6R, TWEAK, and TWEAK-R. microRNA analysis will be conducted using individual Taqman® probes (Applied Biosystems) or microarray (Qiagen), assessing microRNA that may be associated with metabolism and inflammation. This microRNA targets will include, but not be limited to, miR-1, miR-23a/b, miR-26, miR-29, miR-34a, miR-103, miR-107, miR-133a/b, miR-146, miR-206, miR-208a, miR-486, and miR-499a.

Expression of microRNA will also be assessed in circulation using Taqman® probes (Applied Biosystems) or microarray (Qiagen). Circulating miRNA will be extracted from 200 µL serum using miRNeasy Serum/Plasma kit, which allows for extraction and purification of small (< 200 nucleotides) cell-free RNA (Qiagen or equivalent). To avoid introduction of potentially contaminating material, prior to RNA extraction serum samples will be centrifuged for 10 min at 4°C to remove cellular debris. Supernatant will be removed and transferred to a new tube without disturbing the pellet. Due to the small amount of RNA in the serum, 3.5 µL of a Spike-In Control (C. elegans miR-39; Qiagen or equivalent) will be added to all samples prior to extraction of RNA to determine the yield of template recovered. After extraction 3 µL of serum RNA will be reverse transcribed using the TaqMan® microRNA RT kit (Applied Biosystems) or equivalent with miRNA-specific stem-loop RT primers pooled in 1X-Tris-EDTA (TE) buffer for a final dilution of 0.05X. A pre-amplification step will be performed after reverse transcription to increase cDNA template using a primer pool of 20 X Taqman® Small RNA Assays (Applied Biosystems) or equivalent for miRNA of interest at 0.05X concentration in 1X TE buffer. All serum miRNA will be normalized to the geometric mean of external (Spike-In Control C. elegans miR-39) and internal controls to allow for both technical and inter-individual normalization (46). Geometric mean of controls will be used to correct for possible outlying values and abundance differences between the different controls (47).

All reverse transcription for mRNA and miRNA, and pre-amplification of serum miRNA will be conducted in a T100™ Thermal Cycler (Bio-Rad, Hercules, CA or similar model). A StepOnePlus™ real-time PCR system (Applied Biosystems) or similar model will be used to perform all mRNA and miRNA analysis. Fold changes will be calculated using the $\Delta\Delta C_T$ method.

Bioinformatics Analysis

microRNA with significant changes in their expression will be uploaded to DNA Intelligent Analysis (DIANA)-miRPath 3.0 (Alexander Fleming Biological Sciences Research Center [BSRC], Athens, Greece; <http://diana.cslab.ece.ntua.gr>) to determine potential molecular pathways that these microRNA have previously been reported to regulate. Relevant Kyoto Encyclopedia of Genes and Genomes (KEGG; <http://www.genome.jp/kegg/>) pathways will be identified using experimentally verified targets from TarBase 7.0 (Alexander Fleming BSRC). Based on findings from this analysis, any additional gene and protein expression of relevant targets will be assessed.

Western Blotting

Approximately 20 mg of muscle will be homogenized in ice-cold buffer (1:10 w/v) containing 50 mM Tris-HCl (pH 7.5), 5 mM Na-pyrophosphate, 50 mM NaF, 1 mM EDTA, 1 mM EGTA, 10% glycerol (v/v), 1% Triton-X, 1 mM DTT, 1 mM benz-amidine, 1 mM PMSF, 10 µg mL⁻¹ trypsin inhibitor and 2 µg mL⁻¹ aprotinin. Homogenate will be centrifuged for 15 min at 10,000 × g at 4°C. Protein concentration of supernatant (lysate) will be determined using 660 nm Protein Assay (ThermoFisher Scientific, Waltham, MA, USA or equivalent). Phosphorylation status and total protein content will be determined by Western blot. Muscle lysates will be solubilized in Laemmli buffer, with equal amounts of total protein (15 µg) separated by SDS-PAGE using precast Tris-HCl gels (Bio-Rad). Proteins will be transferred to polyvinylidene difluoride (PVDF) membranes and incubated with commercially available primary antibodies of intramuscular molecular regulation to include but not limited to AMPKα, p38 MAPK, PGC-1α, SIRT1, CaMK, p53, Akt, IL-6, TNFα, NF-κB, and IKKα/β (Cell Signaling Technology, Danvers, MA,

USA) at 4°C overnight. Labeling will be performed using secondary antibody (anti-rabbit IgG conjugate with horseradish peroxidase; Cell Signaling Technology), and chemiluminescent reagent will be applied (Super Signal, West Pico Kit; Pierce Biotechnology, Rockford, IL, USA or equivalent). Blots will be quantified using the ChemiDoc XRS from Bio-Rad and Image Lab software (Bio-Rad) or similar model. To confirm equal protein loading per well a normalizing protein such as HSP90 or GAPDH will be assessed.

Enzyme Activity

Assays will be conducting using homogenate from Western blotting to include, but not limited to Pyruvate dehydrogenase (PDH) and citrate synthase. PDH activity will be assessed in lysates using a kinetic colorimetric assay (Cat# MAK183; Sigma-Aldrich). Citrate synthase activity will be determined by colorimetric assay combining 10 mL diluted (1:10; 0.1 M Tris HCl, pH 8.1) sample to 150 mL reaction master mix (1 mL DNTB [5,5-dithio-bis-(2-nitrobenzoic acid)], 3 mg acetyl-CoA, and 8 mL 0.1MTris HCl, pH 8.1) and 10 mL 10 mM oxaloacetate. Enzyme activity data will be normalized to run time and sample protein content.

B5.5 Managing Data and/or Human Biological Specimens for this Research

All data and medical information obtained will be considered privileged and held in confidence. Study volunteers will be assigned unique subject identification (ID) numbers that will not contain any personal identifiers such as name, social security number, address, date of birth, zip code, etc. This study subject ID number will be used on all data collection instruments, to include questionnaires, data collection forms, computer records, etc. A number will be assigned as each volunteer is medically cleared for participation. A master list linking the volunteers' names and ID numbers will be kept in a separate locked file in the principal investigator's office, or kept in a computer file with password-protected access restricted to the principal investigator. When the results of the research are published or discussed in conferences, no information will be included that would reveal identity. All samples will be stored using the subject identification number. De-identified samples for isotopic analysis will be shipped on dry ice to (blood) and room temperature (breath) to Metabolic Solutions. All samples will be shipped via FedEx and stored in these laboratories until analyzed. Once samples have been analyzed, there will be no remaining sample for storage other than the archived sample stored at USARIEM. Coded data will be transmitted between the above mentioned laboratories via an encrypted email, a secure file transfer site, or using an approved removable media. Only USARIEM will maintain digital copies of these data.

Only the principal investigator and project coordinator will have access to personal identifiable data. No outside laboratory will have access to identifiable data. Hard copy data records will be stored for a minimum of three years from the time the study is completed. Electronic data records will be maintained for a period of at least ten years after the study has been completed. The master list will be destroyed upon the protocol's closure.

B5.6 Managing Data and/or Human Biological Specimens for Future Research :

De-identified study samples will be stored in -80°C freezer at USARIEM in room 322 or 304 for potential future use and maintained indefinitely. Only personnel assigned to the research study by the principal investigator will have access to samples. The de-identified data and samples will remain under the control of the PI and may be shared with outside collaborators for future research. Any use of the samples outside of this defined protocol will be submitted as a protocol amendment or a new protocol.

B5.7 Devices, Drugs, Dietary Supplements, Nutritional Supplements, And Biologics

B5.7.1 Devices

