Negative hematological adaptations due to prolonged periods of strenuous physical activity may, in part, contribute to declines in physical performance during military operations. Exogenous erythropoietin (EPO) is a potential intervention that may be used to maintain hemoglobin (hgb), hematocrit (Hct), and physical performance during periods of high physical activity. The objective of the current study is to determine the ability of EPO to maintain hgb, Hct, and physical performance compared to baseline measures. Additionally, EPO may result in non-hematological adaptations which increase mitochondria biogenesis and alter substrate oxidation. As such, this study will also assess the influence of EPO on whole-body and skeletal muscle substrate oxidation. Eight healthy physically active individuals will be recruited to participate in this longitudinal trial. After exercise practice sessions, volunteers will complete baseline physical performance (time trial) and substrate oxidation testing. Participants will then receive EPO injections 3 times per week for 4 weeks. Diet and exercise will be controlled during the injection period. Participants will undergo four weeks of an intense physical training exercise program. Every seventh day during the injection period a safety blood sample, assessing hematocrit, will be drawn, and participants will complete a 5 km time trial to determine the time course of changes in physical performance can be detected. After the 4 weeks of EPO injections volunteers will complete the same physical performance and substrate oxidation testing. Substrate oxidation will be assessed during 90-min steady-state load carriage (30% body mass) exercise on a treadmill at $55 \pm 5\%$ of $\text{VO}_{2\text{peak}}$. 6-6-[²H₂] glucose tracer technique and indirect calorimetry will be used measure substrate oxidation. Muscle biopsies will be performed to measure muscle glycogen, enzyme activity, and molecular markers of metabolism and inflammation before, and immediately and 3-hrs post exercise. Multiple blood samples will be collected throughout the study to determine alterations in hemoglobin, hematocrit, and markers of substrate metabolism, and inflammation. All study procedures will occur at USARIEM. The primary risks associated with this study include those associated with EPO injection, exercise, blood draws, and muscle biopsies.

B2. BACKGROUND AND SIGNIFICANCE

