Recognizing the need for more aggressive interventions to the Army has developed the Biomedical Performance Enhancement (BPE) program. One of the goals of this program is to identify pharmaceutical interventions to enhance physical performance. Exogenous erythropoietin (EPO) is one potential intervention that fits within the BPE program to eliminate physiological decrements during military operations. EPO is a hormone produced in the kidney, that stimulates erythropoiesis, production of red blood cells, in bone marrow (16). Stimulation of red blood cell production corrects negative hematological adaptations, increasing hgb concentration and Hct values (16). Exogenous EPO results in higher levels of hgb and Hct compared to placebo (17-19). It is important to note, exogenous EPO requires iron to induce erythropoiesis. Interestingly, administration of exogenous EPO with low systemic iron availability has been reported to reduce circulating hepcidin concentrations by an unknown mechanism, resulting in increased hgb and Hct (20). Furthermore, our laboratory has recently demonstrate that secondary elevations in circulating EPO following exogenous testosterone administration resulted in lower hepcidin and IL-6, and higher hgb and HCT values following 21 days of exercise-induced (~1400 kcal/d) energy deficits compared to placebo while consuming 18 mg/d dietary iron (21);**Table 1**. These finding may suggest that despite reduced iron efflux with overtraining, EPO may still be an effective intervention to maintain hgb, Hct, and physical performance. However, whether elevated IL-6 and hepcidin concentrations with overtraining suppress the effectiveness of exogenous EPO is unknown.

Table 1: Hematological adaptations following 21 days of energy deficit

	Placebo	Testosterone		
	Energy Balance	Energy Deficit	Energy Balance	Energy Deficit
EPO (mIU/mL)	8.8 (7.6, 9.9) ^a	8.5 (7.1, 9.8) ^a	8.4 (7.2, 9.6) ^a	11.3 (9.9, 12.8) ^b
Hgb (g/L)	144 (142, 147) ^a	138 (136, 141) ^b	145 (143, 148) ^a	145 (142, 148) ^{a*}
HCT (%)	42.8 (42.0, 43.6) ^a	41.5 (40.7, 42.3) ^a	42.9 (42.1, 43.7) ^a	43.6 (42.7, 44.4) ^{a*}
Hepcidin (ng/mL)	8.1 (6.6, 9.8) ^{ab}	10.1 (8.5, 11.6) ^a	8.6 (7.0, 10.3) ^a	5.1 (3.4, 6.7) ^{b*}
IL-6 (pg/mL)	8.5 (6.2, 10.8) ^a	10.2 (7.9, 12.5) ^a	9.2 (6.9, 11.6) ^a	8.5 (6.1, 10.9) ^a

[figure not shown]
Values mean (95% confidence interval). Data not sharing the same letters are different; $P < 0.05$.

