adaptations due to reduced iron efflux during overtraining to aid in the maintenance of physical performance has not been explored.

B3. MILITARY RELEVANCE

This study supports the Military Operational Medicine Research Program's Physiological Health and Performance Program Area under the BPE Work Unit. The BPE Work Unit is intent is to execute basic and applied research aimed at identifying and develop biomedical strategies and solutions that safely and ethically enhance Warfighter physical, cognitive, sensory and behavioral performance in training and operational environments, enabling lethality and overmatch. The proposed work aligns to the Physiological Health and Performance Strategic Plan Technical Challenge 1.1.1.1: Identify pharmacological enhancement protocols improving specific task performance under operational stress.

B4. OBJECTIVES/SPECIFIC AIMS/RESEARCH QUESTIONS

Objective

1. Determine the effects of EPO on hematological adaptions compared to baseline during 4 weeks of overtraining.
2. Determine the time course change in physical performance (time trial) with EPO compared to baseline.
3. Assess the influence of EPO non-hematological adaptation (whole-body and skeletal muscle substrate oxidation and glucose turnover) following 4 weeks of overtraining compared to baseline.

Hypothesis

1. Hemoglobin and hematocrit will be maintained with EPO during 4 weeks of overtraining.
2. Physical performance will be maintained with EPO during 4 weeks of overtraining.
3. EPO will increase whole body and skeletal muscle fat oxidation, and reduce reliance on endogenous glucose store following 4 weeks of physical training.

B5. RESEARCH PLAN

B5.1 Research Design

This study will be a longitudinal trial.

B5.2 Research Subjects/Population(s)

B5.2.1 Subject Population(s)

Subject population will be military or civilians representative of active duty male and female service members, being in good health and recreationally active.

B5.2.2 Number of Subjects, Records, and/or Specimens

A total of 8 volunteers will be required to achieve sufficient statistical power. To complete testing on 8 volunteers, we estimate we will need to enroll 60 individuals. All screening will stop once complete data has been collected on 8 volunteers. Records and specimen collection are described in the Research Procedures and Data Collection sections. During briefings and consenting potential participants will be informed that even though they may be eligible and want

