Study Design Overview: Healthy physically active individuals will be recruited to participate in this longitudinal trial. After baseline assessments of body composition, resting metabolic rate (RMR), $\text{VO}_{2\text{peak}}$ and exercise familiarization; volunteers will complete physical performance and substrate oxidation testing (Figure 3). Physical performance will be assessed using time trial. Substrate oxidation will be assessed by volunteers performing 90-min of steady-state load carriage (30% body mass) exercise on a treadmill at $55 \pm 5\%$ of their $\text{VO}_{2\text{peak}}$. 6-6-[$^2\text{H}_2$] glucose will be used as a tracer to assess glucose turnover. Indirect calorimetry will be used to determine carbohydrate and fat oxidation. Muscle biopsies will be performed to measure muscle glycogen, enzyme activity, and molecular markers of substrate metabolism before, immediately after, and 3-hrs post exercise. Multiple blood samples will be collected on substrate oxidation protocol days. To minimize carry over effects of muscle biopsies on subsequent exercise performance, volunteers will not exercise for 3 days. During the first two days of this period, volunteers will undergo carbon monoxide (CO) rebreathing to measure Hgb mass and blood volume. Volunteers will then receive EPO injections 3 times a week for 4 weeks. During the injection period all volunteers will have safety blood draws to assess Hct once a week. Volunteers will also complete a physical performance test once a week to determine time course change in performance with EPO compared to baseline. Exercise training will be controlled during the injection phase, consisting of a combination of endurance- and resistance-type exercise. During the final week of the injection phase body composition, resting metabolic rate (RMR) and $\text{VO}_{2\text{peak}}$ will be reassessed. At the end of the 4-week injection phase volunteers will complete a final physical performance test and substrate oxidation protocol, followed by two CO rebreathing tests on subsequent days. All food and beverages (except water) will be provided to volunteers beginning at the pre injection physical performance and substrate oxidation through the duration of the study. All data collection will occur at USARIEM.

Figure 3: Study Timeline

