For glucose kinetic analysis, the tracer/trace ratio (6,6-[2 H₂] glucose/glucose) will be measured on the pentaacetate derivative by gas-chromatography-mass spectrometry (Metabolic Solutions, Inc., Nashua, NH). Credentialled personnel performing venipuncture and/or venous catheterization will be listed on the DOA log with code "S and T."

Carbon Monoxide Rebreathing (credentialled procedure): The optimized CO-rebreathing technique (42, 43) will be used to assess total hemoglobin mass (Hbmass, the total mass of hemoglobin in the circulation) and blood volume. Volunteers will sit for 20 minutes for postural control and then a venous blood sample will be collected to assess Hb and Hct. Baseline carboxyhemoglobin (%HbCO) will be

assessed from an arterialized capillary blood sample (finger stick) using a hemoximeter (Radiometer, OSM3, Denmark, or similar). The volunteer will then breathe into a CO detector (Draeger Pac 7000, Draeger, Lubeck, Germany, or similar) to assess end-tidal CO. Next, the volunteer will be administered a bolus of CO (99.99%; men: 1.0 ml/kg body mass; women: 0.8 ml/kg body mass; if body mass index is > 30 kg/m² convert body mass to BMI of 25 kg/m²) into a custom built, closed-circuit spirometer (Spico-CO Respiration-Applikator, Blood Tec, Germany or similar) followed with 100% oxygen from a 3L bag and rebreathe for two minutes. Once the 2 minutes are complete, the volunteer will return to breathing room air. Four minutes after the initial CO inhalation, post-rebreathing end-tidal CO concentration will be assessed using a CO detector. Seven minutes after the initial CO inhalation, an arterialized capillary sample will be collected to determine the post-rebreathing increase in %HbCO. Female volunteers will complete a pregnancy test prior to CO rebreathing measurements. Female staff members will oversee pregnancy tests. Credentialed personnel performing CO rebreathing will be listed on the DOA log with code "W."

B5.4 Data Collection

Data Element/Variable	Source	Operational Specification
Anthropometric data	Direct measurement	Height, weight, body composition
Dietary intake	Log and direct measurement	Habitual and controlled energy, protein, carbohydrate, and fat intake
Physical activity	Log and direct measurement	Normal and controlled physical activity habits including type of exercise and duration
Substrate oxidation	Blood and breath	Glucose turnover, carbohydrate, and fat oxidation
Physical performance	Direct measurement	TTE

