5.7.1.1 FDA-approved device being used in this research according to the approved labeling

DEXA, DPX-IQ, Lunar Corporation, True Max 2400, Parvomedics, Sandy, Utah, USA, Polar Electro Inc, Oulu, Finland

5.7.1.2 FDA-approved device being used in this research in a manner other than its approved labeling: N/A

B5.7.2 Drugs

B5.7.2.1 FDA-approved and used in accordance with the approved labeling

B5.7.2.2 FDA-approved and used in a manner not in accordance with its approved labeling:
PROCRIT, EPOETIN ALFA, Janssen Products, LP, Titusville, NJ, USA

B5.7.2.3 Any drug not approved by the FDA: N/A

B5.8 Statistical Analysis

B5.8.1 Sample Size Estimation

Based on results for multiple outcomes across different studies (**Table 4**) a sample size of 8 is required to statistical significance.

Table 4: Previous study effect sizes

Study	Outcome	Delta	Effect Size	Sample Size
Thomson et al. (18)	TTE	10 ± 6	1.40	7
Plenge et al. (24)	Hct	5.1 ± 3	1.56	7
Caillaud et al. (19)	CHO Oxidation	0.7 ± 0.3	1.24	4
Caillaud et al. (19)	Fat Oxidation	0.2 ± 0.05	3.51	2

B5.8.2 Data analysis

Statistical analyses will be conducted using either SPSS (IBM Corp. Armonk, NY), SAS 9.3 (SAS Institute Inc., Carey, NC), or equivalent. Common descriptive statistics will be used to describe volunteer characteristics. Shapiro-Wilk tests will be used to determine normality of data. Paired t-tests will be used to assess phase effects (PRE vs. POST injection) for glucose turnover, and substrate oxidation. Repeated measures ANOVA will be used to assess main effects of time for physical performance. Mixed-model repeated measure ANOVA will be used to assess main effects of phase (PRE vs. POST injection), time and their interaction for blood analytes and muscle molecular analysis. If interactions are significant, appropriate post-hoc correction will be used to examine these relationships. Correlation coefficients and multiple regression analysis will be used to evaluate relationships between study outcome measures. The alpha level will be adjusted for multiple comparisons, with the level for statistical significance set at $P < 0.05$.

SECTION C: HUMAN RESEARCH PROTECTIONS

C1. RECRUITMENT AND CONSENT

C1.1 Identification and Selection of Subjects

Volunteers will be recruited from the federally and non-federally employed civilian population, the Natick Human Research Volunteer (HRV) Pool, and NSSC active duty military personnel.

C1.2 Recruitment Process

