18 March 2025

PROTOCOL TITLE: Impact of erythropoietin on hematological adaptations and physical performance

NCT: 05078138

B5.8.1 Sample Size Estimation

Based on results for multiple outcomes across different studies (**Table 1**) a sample size of 8 is required to statistical significance.

Table 1: Previous study effect sizes

Study	Outcome	Delta	Effect Size	Sample Size
Thomson et al.	TTE	10 ± 6	1.40	7
Plenge et al.	Hct	5.1 ± 3	1.56	7
Caillaud et al.	CHO Oxidation	0.7 ± 0.3	1.24	4
Caillaud et al.	Fat Oxidation	0.2 ± 0.05	3.51	2

B5.8.2 Data analysis

Statistical analyses will be conducted using either SPSS (IBM Corp. Armonk, NY), SAS 9.3 (SAS Institute Inc., Carey, NC), or equivalent. Common descriptive statistics will be used to describe volunteer characteristics. Shapiro-Wilk tests will be used to determine normality of data. Paired t-tests will be used to assess phase effects (PRE vs. POST injection) for glucose turnover, and substrate oxidation. Repeated measures ANOVA will be used to assess main effects of time for physical performance. Mixed-model repeated measure ANOVA will be used to assess main effects of phase (PRE vs. POST injection), time and their interaction for blood analytes and muscle molecular analysis. If interactions are significant, appropriate post-hoc correction will be used to examine these relationships. Correlation coefficients and multiple regression analysis will be used to evaluate relationships between study outcome measures. The alpha level will be adjusted for multiple comparisons, with the level for statistical significance set at $P < 0.05$.

References

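### Hypotheses 1 and 2 predict that Hgb, Hct and performance are maintained, but only difference tests are planned, so a near-zero change could not support them

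*Protocol*

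**What the plan says.** The protocol's opening summary frames the study around maintenance: "The objective of the current study is to determine the ability of EPO to maintain hgb, Hct, and physical performance compared to baseline measures". B4 repeats this in Hypothesis 1 ("Hemoglobin and hematocrit will be maintained with EPO during 4 weeks of overtraining") and Hypothesis 2 ("Physical performance will be maintained with EPO during 4 weeks of overtraining"). Baseline is the reference, but no tolerated loss, margin or confidence-interval rule is given. The numbered Objectives 1 and 2 in B4 are worded differently. They ask what effect EPO has, and how performance changes over time, relative to baseline.

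The planned analyses are the same in both documents. For performance, protocol B5.8.2 says "Repeated measures ANOVA will be used to assess main effects of time for physical performance". For blood analytes, which include Hgb and Hct in protocol Table 3, SAP B5.8.2 says "Mixed-model repeated measure ANOVA will be used to assess main effects of phase (PRE vs. POST injection), time and their interaction". Significance is set at P<0.05, with an unspecified adjustment for multiple comparisons. No equivalence or non-inferiority analysis is planned.

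The data for a direct pre-to-post estimate will exist. B5.3 schedules a 5 km time trial before the injections, and "At the end of the 4-week injection phase volunteers will complete a final physical performance test and substrate oxidation protocol". At each CO-rebreathing test "a venous blood sample will be collected to assess Hb and Hct", and there are two such tests on separate days in each phase.

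**The concern.** A difference test can show that something changed. It cannot show that nothing of importance changed. If EPO raises Hct and improves 5 km time, the planned tests will say so and the hypotheses are supported. If EPO only cancels a fall caused by the training, the true change is near zero, which is the literal meaning of maintained. The expected result is then P>0.05, and the plan gives no route from there to a conclusion.

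The protocol leaves this outcome open. B2 says that "whether elevated IL-6 and hepcidin concentrations with overtraining suppress the effectiveness of exogenous EPO is unknown". For performance there is a further reason not to assume a clear improvement: the sizing row is TTE, while the test in B5.3 is a 5 km time trial, for which no expected effect or SD is given.

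At stake is whether two of the three hypotheses can be answered if the change is small.

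**Working it through.** **Inputs.** n = 8, one group (B5.2.2, B5.1). Alpha 0.05 (B5.8.2), taken as two-sided because sidedness is not stated. Table 4 of the protocol (Table 1 of the SAP): Hct 5.1 ± 3, effect size 1.56; other effect sizes 1.40 (TTE), 1.24 (CHO oxidation) and 3.51 (fat oxidation). The ± is unlabelled; it is read here as the SD of change. All figures are for a simple paired comparison without alpha adjustment. The planned ANOVA models and any adjustment would change them.

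**1. The plan's own figure.** Power of a paired t-test = P(|T'| > t(0.975, n−1)), where T' is noncentral t with noncentrality d√n. Power is not stated, so 80% is assumed. The smallest n is 7 (d = 1.40), 6 (1.56), 8 (1.24) and 3 (3.51). The largest is 8, which matches the stated total. The table's own row values are 7, 7, 4 and 2. The CHO row does not follow from its effect size, but that is a separate matter. What counts here is that the trial is sized to detect a difference.

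**2. If the assumed Hct rise occurs.** At n = 8:
- d = 1.56: noncentrality 1.56 × 2.828 = 4.41, power 0.964.
- d = 5.1/3 = 1.70: noncentrality 4.81, power 0.983.

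There is no gap in this case.

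**3. Precision.** The 95% CI half-width is t(0.975, 7)/√8 = 2.365/2.828 = 0.836 SD of the within-person change. For Hct with an SD of 3 this is 0.836 × 3 = 2.51 points.

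**4. Power to detect a true decline, n = 8.**

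| True decline (SD of change) | Noncentrality | Power |
|---|---|---|
| 0.5 | 1.41 | 23.2% |
| 0.8 | 2.26 | 49.6% |
| 1.0 | 2.83 | 68.1% |

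**5. If the true change is zero.** By construction 95% of results are non-significant. Among these, the share whose 95% CI still includes a decline of m SD is P(x̄ − 0.836s < −m, given |x̄| < 0.836s), with x̄ ~ N(0, 1/8) and 7s² ~ χ² on 7 df. Numerical integration gives 78.3% for m = 0.5, 55.5% for m = 0.75 and 31.5% for m = 1.

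**6. What a margin rule would deliver.** Conclude maintained if the one-sided confidence limit on the worse side excludes the margin m. At zero true change the chance is P(T' > t(1−α, 7)) with noncentrality m√8.

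| Margin (SD of change) | One-sided 0.05 | One-sided 0.025 |
|---|---|---|
| 0.5 | 35.7% | 23.1% |
| 0.75 | 60.5% | 44.8% |
| 1.0 | 81.5% | 68.1% |
| 1.25 | 93.6% | 85.6% |

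**The case against.** The best defence is that the documents mostly expect a rise. B2 says EPO gives higher Hgb and Hct than placebo, B5.3 says this regimen has produced hematological adaptations and better performance, and the sample size rests on increases. Objectives 1 and 2 are neutral questions about change, and difference tests suit them. C8.4 adds that the trial is not meant as a well-controlled study for a new indication. All of this stands. It confines the gap to a small observed change and to the wording of the hypotheses and the opening summary. It does not close the gap, because B2 itself treats a blunted EPO response as an open question.

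A reader might go further in four ways that the documents do not support:
- That the sponsor intends to read non-significance as maintenance. Nothing says so; the plan simply offers no other route when the change is small.
- That a non-significant result would usually conceal a sizeable decline. At 1 SD the share is 31.5%, well under half. Nothing shows that 0.5 SD is sizeable, since no SD of change is given for Hgb or 5 km time.
- That 8 volunteers is the root fault. If the SD of Hct change were 1 point, the half-width would be 0.84 points. The missing definition matters more than n.
- That the 6 g/L Hgb difference on placebo in protocol Table 1 (144 against 138) bounds the untreated decline or supplies a margin. It contrasts energy balance with energy deficit in another study, so the decline here could be larger or smaller.

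**Conclusion.** The concern holds in a conditional form. The hypotheses are phrased as maintenance and the tests as difference, so the plan can support Hypotheses 1 and 2 through a significant improvement but not through a near-zero change. In the near-zero case a simple paired comparison leaves a 95% interval of ±0.84 SD of change, and real declines of 0.5 to 1 SD would be missed between 77% and 32% of the time. These figures assume 8 completers, approximately normal changes and an unadjusted two-sided 0.05. Whether declines of that size matter cannot be settled from the documents. This should be fixed: it is inexpensive, and a rule chosen after the results are known would be post hoc.

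**What to change.** In B5.8.2 of the protocol and the SAP:

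1. Keep the planned tests, including the repeated-measures analysis of the performance time course. Add the mean change from baseline to the end of the injection phase, with its 95% CI, for Hgb, Hct and 5 km time. State in advance how the two CO-rebreathing samples per phase are combined.
2. State that a non-significant result will not be read as maintained. Base any such statement on the CI limit on the worse side (lower for Hgb and Hct, upper for time). Describe it as stability from baseline, because without a control group it cannot be credited to EPO.
3. If a formal verdict of maintained is wanted, fix a justified margin in absolute units, and its one-sided alpha, before the data are analysed. Otherwise reword Hypotheses 1 and 2 as estimation of change.

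The cost is wording only, with no new volunteers or measurements. The drawback is that a near-zero result will often be reported as inconclusive. As the last table in the working shows, a margin of 0.5 SD would yield a verdict of maintained only 35.7% of the time at one-sided 0.05, even with no true change.
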